University of Chicago Medical Center Research Protocol

Principal Investigator: [name] – Pediatrics/Neonatology &
Medicine/Gastroenterology

Other Investigators: [name], MD – Pediatrics/Neonatology
[name] – Pediatrics/Infections Diseases

Study Title: Antibiotic stewardship and protection of the developing preterm infant microbiome

ABSTRACT:

Fear of early-onset sepsis (EOS) has led to nearly universal initiation of empiric antibiotics at birth in preterm infants. While the risk of morbidity and mortality from EOS is high, the frequency is low at 0.98 per 1000 live births (Stoll et al 2011). Evidence shows that there are significant risks involved with prolonged antibiotic therapy, including necrotizing enterocolitis, invasive fungal infection, and even death. Furthermore, antibiotics alter the microbiome, which is increasingly being recognized as a key determinant of health and disease. The development of the microbiome begins at birth; the very time empiric antibiotics are begun in the majority of preterm infants. We hypothesize that antibiotic stewardship principles can be used to limit empiric antibiotic use at birth in preterm infants, thus leading to protection of the developing microbiome and improved clinical outcomes.

I. Aim and Hypotheses

Preterm infants are frequently started on empiric antibiotics at birth due to the risk of early onset sepsis (EOS). While the risk of morbidity and mortality from EOS is high, the frequency is low at 0.98 per 1000 live births (Stoll et al 2011). There are risks involved with antibiotic therapy including disseminated fungal infection, neonatal necrotizing enterocolitis, and alteration of the gastrointestinal microbiome (Nash et al 2009). We hypothesize that antibiotic stewardship principles can be used to limit empiric antibiotic use at birth in preterm infants, thus leading to protection of the developing microbiome and improved clinical outcomes.

Aim 1: Implement an antibiotic stewardship program to limit initial empiric antibiotic administration in a pilot study group of 30 preterm patients, 28-34 weeks gestation.

Aim 2: Evaluate outcomes in infants who do, or do not, receive empiric antibiotics at birth. Blood culture results, clinical outcomes, length of stay, total days of antibiotics received during NICU admission, and microbiome development from birth until hospital discharge will be examined.

II. Background and Rationale

A. Background:

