Greater than 12% of infants in the United States are born premature and may begin their lives within the neonatal intensive care unit (Matthews et al). Within this population, the evaluation and treatment for early-onset sepsis (EOS) is an ongoing controversy. EOS remains the leading cause of morbidity and mortality in neonates with a rate of 0.98 per 1000 live births (Stoll et al). Infants admitted to NICUs are frequently started on empiric antibiotics due to the risk of EOS. Although the CDC has released algorithms for the evaluation of EOS for all newborns, without a lower gestational age limit indicated to which they apply, clinical experience has shown that nearly all premature infants receive empiric antibiotics (Verani et al 2010). Recent algorithms by the AAPs Committee on the Fetus & Newborn recommend discontinuing empiric therapy at 48 hours with negative cultures in preterm infants (Polin et al 2012). However, although it has been shown that discontinuing antibiotics when cultures are negative in asymptomatic ELBW infants does not compromise clinical outcomes, they often receive prolonged antibiotic treatment courses (Cordero & Ayers 2003). Furthermore, Kuppala et al (2011), studied very low birth weight (VLBW) infants, and found that within their population, 16% did not receive empiric antibiotics. For those who were treated, each day of initial empiric antibiotic therapy significantly increased the odds of developing late-onset sepsis (LOS), NEC or death, and for infants who had received any initial empiric antibiotic exposure, the number needed to harm was 3.

Within our unit, there were 794 admissions in 2014. Of these, 196 were within our study's target age range of 28-34 6/7 weeks of gestation at birth. While there were no positive blood cultures at birth within this gestational age range, only 6 of these 196 patients did not receive empiric antibiotics at birth. Additionally, of the 190 that were treated, 43 were treated beyond the standard 48-hour rule-out-sepsis recommendations.

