- 1) Signs of clinical illness within the first 3 hours of life (Escobar et al 2014):
 - a. 5-minute Apgar <5
 - b. Requiring vasoactive drugs
 - c. Seizures
 - d. Significant respiratory distress requiring supplemental oxygen >40%
- 2) I:T Ratio of >0.2 on initial CBC
- 3) Congenital anomalies, including renal anomalies requiring serum antibiotic level monitoring.

30 patients who meet inclusion criteria will be enrolled for randomization. Parents of infants that may be eligible will be consented prior to the birth if the infant meets the inclusion criteria at the time of birth, they will be randomized into one of the study groups. Parents who consent will be notified whether or not their child met inclusion criteria and were randomized in the study. They can choose to withdraw their child from the study at any time.

If infants are not determined to be low-risk at the time of birth, and do not meet the inclusion criteria for randomization, they will remain in the study for stool sample analysis and data collection. Their medical management will be ordered by the primary care team, including the possible administration for antibiotics at birth.

The study design will be a randomized, double-blinded study where all consented infants who meet the inclusion criteria will undergo a standard limited sepsis evaluation at birth, consisting of a blood culture and complete blood count with differential, as recommended in the CDC guidelines for prevention of GBS sepsis. Following evaluation, infants will be randomized. The control group of infants will receive current standard of care empiric antibiotic coverage with ampicillin and gentamicin. The infants in the intervention group will receive placebo at the same dosing intervals of the routine antibiotic coverage. Antibiotics, or placebo, will be discontinued after 48 hours, at which time the blood culture would be reported as negative at 48 hours, consistent with the standard of care rule out sepsis evaluation. Each treatment group, control and intervention, will have 15 study participants. We will further aim to have half in each treatment group to be under the gestational age of 32 weeks and half older than 32 weeks. Multiples will be randomized to the same treatment group. We will consent up to 80 patients in order to have 30 that will meet randomization criteria.

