If at any time during the initial 48 hour trial period an infant shows clinical signs of sepsis, as defined below, or the initial blood culture becomes positive, the infant will be unblinded. Repeat evaluation will be performed, and antibiotics will either be initiated for those in the intervention group, or appropriately broadened, per the discretion of the medical team, for those already receiving antibiotics. These patients will remain in the study for intention-to-treat analysis

Signs of clinical sepsis for which to unblind infant from the study and repeat evaluation (Hofer et al 2012, Bekhof et al 2013)

- Temperature Instability (Rectal, $>38.5^{\circ}\text{C}$, $<36.0^{\circ}\text{C}$ or $>1.5^{\circ}\text{C}$ change in 3 hours)
- Increased respiratory support of more than 20% increase in oxygen
- Pale/dusky skin tones
- Prolonged capillary refill time
- Lethargy
- Development of Seizures
- Requiring vasoactive medications for cardiovascular support
- Other signs of illness per the discretion of the managing team

Throughout their entire hospitalization, all infants will receive routine neonatal care per the medical team managing the patient.

During the entire hospitalization of the patients, daily stool samples will be collected from the infant diaper as available from spontaneous defecation, for analysis of the fetal microbiota through 16S rRNA gene-based analysis, as previously described by Wang, et al (2009). Through this stool analysis, the development of the fetal microbiome from birth through discharge will be examined and compared between the infants who do, or do not, receive empiric antibiotics at birth. Some of the stool samples will also be shared with the investigators at the University of Guelph in Ontario, Canada for further analysis, including identification of certain metabolites and antibiotic levels. The samples that are sent will be deidentified. Parents may be contacted when the infants are 18 months of life to answer a short health questionnaire about hospitalizations and chronic illnesses, as well as to provide stool samples for further analysis to determine if the differences persist once they are outside of the hospital environment. All supplies for stool samples and return postage will be provided to the parents. Parents will receive a small monetary compensation (\$15 gift card) for returning the questionnaire and stool sample.

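### The outcome comparison is defined by antibiotic receipt at birth rather than by randomised arm, and its wording lets in infants who were never randomised

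*Protocol*

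**What the plan says.** The protocol states its outcome comparison in two places, both times by exposure.

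- Section I, Aim 2: "Evaluate outcomes in infants who do, or do not, receive empiric antibiotics at birth".
- Section III, Methods, stool analysis: microbiome development from birth to discharge is to be "compared between the infants who do, or do not, receive empiric antibiotics at birth".

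The later list of clinical outcomes taken from the medical record names no comparison groups.

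Section III, Methods, also describes two populations. The randomised one is small: "Each treatment group, control and intervention, will have 15 study participants". The second consists of consented infants who turn out not to be low-risk and do not meet the criteria for randomisation. Of these it says "they will remain in the study for stool sample analysis and data collection", and then "Their medical management will be ordered by the primary care team, including the possible administration for antibiotics at birth". The consent target is "We will consent up to 80 patients in order to have 30 that will meet randomization criteria".

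The only reference to analysis as assigned concerns randomised infants who are unblinded within 48 hours for signs of sepsis or a positive culture: "These patients will remain in the study for intention-to-treat analysis".

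**The concern.** The trial randomises so that infection risk is balanced, in expectation, between infants given antibiotics and infants given placebo. A comparison by receipt, open to every enrolled infant, gives that balance away. The non-randomised infants are in the study because they were not judged low-risk, and whether they get antibiotics is a clinical decision. In a unit that treats nearly every infant of this gestation, almost all of them would join the exposed group. The unexposed group would remain mostly low-risk infants randomised to placebo. A difference in microbiome, length of stay or morbidity could then reflect infection risk rather than antibiotics, and the data could not separate the two. No direction of bias is claimed for the microbiome endpoints.

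**Working it through.** **The protocol's own figures.** 15 + 15 = 30 randomised, as stated. Non-randomised infants number at most 80 − 30 = 50, or 62.5% of those consented. No alpha, power or effect size is given, so there is no power calculation to reproduce.

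**Treatment rate for non-randomised infants.** The protocol gives none. The Background reports that in 2014, among admissions at 28 to 34 6/7 weeks, "only 6 of these 196 patients did not receive empiric antibiotics at birth". That is 190/196 = 96.9% treated. Carrying this rate over is an assumption, and it is varied below.

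**Composition of the groups as worded.** With n non-randomised infants, a share r of them treated:

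- exposed E = 15 + n·r
- unexposed U = 15 + n·(1 − r)
- non-randomised share = n·r/E among the exposed and n·(1 − r)/U among the unexposed

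For n = 50 and r = 0.969: E = 15 + 48.5 = 63.5 and U = 15 + 1.5 = 16.5. The shares are 48.5/63.5 = 76% and 1.5/16.5 = 9%.

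**Spurious shift.** Assume antibiotics have no effect and non-randomised infants differ from randomised ones by d (in SD) on one continuous outcome. The expected difference between the groups is d × (share in exposed − share in unexposed). For n = 50, r = 0.969 and d = 0.5 this is 0.5 × (0.764 − 0.093) = 0.34 SD.

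**False-positive rate.** The calculation uses a two-sided 5% two-sample t-test and independent infants. The standard error is √(1/63.5 + 1/16.5) = 0.276 SD and the noncentrality 0.336/0.276 = 1.22 on 78 degrees of freedom, giving a rejection rate of 22%.

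| n | r | d (SD) | Exposed v unexposed | Non-randomised share | Shift (SD) | False positives |
|---|---|---|---|---|---|---|
| 50 | 96.9% | 0.5 | 63.5 v 16.5 | 76% v 9% | 0.34 | 22% |
| 20 | 96.9% | 0.5 | 34.4 v 15.6 | 56% v 4% | 0.26 | 13% |
| 10 | 96.9% | 0.5 | 24.7 v 15.3 | 39% v 2% | 0.19 | 9% |
| 50 | 96.9% | 0.25 | 63.5 v 16.5 | 76% v 9% | 0.17 | 9% |
| 50 | 96.9% | 1.0 | 63.5 v 16.5 | 76% v 9% | 0.67 | 67% |
| 50 | 75% | 0.5 | 52.5 v 27.5 | 71% v 45% | 0.13 | 8% |
| 50 | 50% | 0.5 | 40 v 40 | 62.5% each | 0 | 5% |

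Allowing for the extra variance of mixed groups changes these little, except at d = 1.0, where 67% falls to about 60%.

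**By assigned arm.** The comparison is 15 v 15 with no non-randomised infants in either group, so this source of shift is zero in every row.

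**The case against.** Among randomised infants, the exposure wording can be read as a plain-language name for the two arms: one gets empiric antibiotics from birth, the other placebo. An infant on placebo who later starts antibiotics for signs of sepsis was not treated empirically at birth, and the protocol keeps unblinded infants for intention-to-treat analysis. Aim 1 speaks of a pilot group of 30, the design is called randomised and double-blinded, and no sentence says the two populations will be combined. A statistical analysis plan that is not shown may define the analysis sets. The size of the effect depends on a risk difference that the protocol does not supply: at 0.1 SD and 50 non-randomised infants, the false-positive rate is only 5.7%. Fifty is a ceiling, the 2014 rate may not apply to all those not randomised, and a single-outcome t-test stands in for repeated 16S data.

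Much of this is fair. Receipt at birth and assigned arm largely coincide within the randomised set, pooling is not expressly planned, and the figures can only illustrate. But none of these points keeps the non-randomised infants out. They fit the stated groups, they supply the same kinds of data, and nothing gives them a separate role. The intention-to-treat sentence covers only unblinded randomised infants and sets no analysis population. Nor is this merely a detail left to a later document: the protocol states the comparison, and an analysis plan restricted to assigned arms would have to depart from the wording of Aim 2.

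**Conclusion.** The concern holds and should be fixed. Both statements of the comparison define groups by receipt of antibiotics without limiting them to randomised infants, while up to 50 infants treated at clinicians' discretion remain in the study. Taken literally, this gives an observational contrast confounded by infection risk. That conclusion rests on the text alone.

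The size rests on assumptions: how many non-randomised infants there are, what share of them is treated, and how far they differ from the randomised infants. At the cap of 50, the 2014 treatment rate and a 0.5 SD difference, the false-positive rate is about 22% instead of 5%. Across the cases in the table it runs from 5% (half of them treated) to 67% (a 1.0 SD difference, about 60% with mixed-group variance). Confidence is medium, because the investigators may already intend an analysis by arm.

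**What to change.** Reword two sentences and add one.

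- Aim 2: evaluate outcomes in infants randomised to empiric antibiotics or to placebo, by assigned arm.
- Methods, stool analysis: compare microbiome development between infants randomised to antibiotics and infants randomised to placebo, by assigned arm (intention-to-treat).
- Added sentence: non-randomised infants are reported as a separate descriptive cohort, and any comparison by antibiotic receipt that includes them is a secondary observational analysis.

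No infants, samples or procedures change, and no clinical rule is touched. The cost is nominal precision relative to a pooled analysis. The standard error of a mean difference is √(2/15) = 0.37 SD for 15 v 15, against 0.28 SD for 63.5 v 16.5. The difference detectable with 80% power at two-sided 5% is about 1.06 SD against 0.78 SD. These figures treat infants as independent. Because multiples share an arm, the true standard error for 15 v 15 is probably somewhat larger. The precision given up belongs to a confounded contrast.

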In addition to analyzing the microbiome, blood culture results, clinical outcomes (chronic lung disease, retinopathy of prematurity, intraventricular hemorrhage, death, NEC), length of stay, initiation and type of feeds, feeding tolerance and total days of antibiotic use will be examined through review of the EMR.

Monitoring:

The study team will report all events in accordance with IRB policies and procedures. Events not meeting reporting criteria will be provided at the time of continuing review.

All enrolled infants will be continuously monitored for signs of infection during the first 48 hours of life, as well as through the remainder of their hospitalization due to their admission in an ICU setting. Because of the small size of this pilot study, if there is any adverse event or safety concern, it will be immediately analyzed.

In addition, we will meet to evaluate for adverse events and safety for every 3 patients that are enrolled into the randomization portion of the study (weekly may be impractical due to the varied response in consent among our patient population - there may be many weeks without new study participants). This will result in 10 meetings throughout the course of the pilot study. We will also invite the NICU's medical director to participate in these meetings to ensure patient safety.

We will not be performing an interim efficacy analysis. This is due to the small sample size and single site design, as well as their prematurity of our study population which requires prolonged hospitalization. The study subjects will be continuously and closely monitored due to their gestational age and hospitalization within an intensive care setting. If at any time a patient becomes ill during the initial 48 hours, they will become unblinded. If it is a

repeated pattern that only those patients who are receiving placebo are becoming ill, the safety of the study will be reevaluated by the study team.

If three patients from this group develop sepsis in the first 48 hours, the trial will end.

Works Cited

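### The only rule that ends the trial counts placebo-group sepsis for 48 hours, so early sepsis that first shows clearly later does not count (minor, cheap to fix)

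*Protocol*

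**What the plan says.** All of the relevant text is in the Protocol.

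- **Stopping rule** (III. Research Plan, Monitoring): "If three patients from this group develop sepsis in the first 48 hours, the trial will end". The preceding sentence is about infants receiving placebo, so the count is of that arm. The rule does not say from when the 48 hours run.
- **Study drug** (III. Research Plan, Methods): "Antibiotics, or placebo, will be discontinued after 48 hours".
- **Unblinding for illness**: Methods opens the provision with "If at any time during the initial 48 hour trial period an infant shows clinical signs of sepsis", and Monitoring repeats it: "If at any time a patient becomes ill during the initial 48 hours, they will become unblinded".
- **Other safeguards** (Monitoring): infants are watched for infection "during the first 48 hours of life, as well as through the remainder of their hospitalization"; "if there is any adverse event or safety concern, it will be immediately analyzed"; the team meets for every 3 randomized infants, with the NICU medical director invited; and if a repeated pattern emerges that "only those patients who are receiving placebo are becoming ill, the safety of the study will be reevaluated by the study team".
- **Unit experience** (II. Background and Rationale): among 196 infants admitted in 2014, "there were no positive blood cultures at birth within this gestational age range". All but 6 of the 196 received empiric antibiotics.

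**The concern.** The harm that this design could cause is early sepsis in an infant from whom standard empiric antibiotics were withheld. That hazard does not end when placebo ends, because the infant is still untreated. Forty-eight hours is the dosing period and the time at which the birth culture is reported. The protocol gives no reason why it should also be the limit for counting harm.

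An onset clearly after the window bears on the same question as an onset inside it, but only the second moves the trial towards its stated stop. The unblinding provision for illness closes at the same point. For a later case the text therefore gives neither a place in the count nor a stated route to the assignment. Recognizing a placebo-only pattern would also need that assignment. Ending the trial over such cases is left to judgement, possibly without knowing which arm they came from.

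**Working it through.** **1. The provisions side by side**

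| Provision | Period covered | Ends the trial? |
|---|---|---|
| Three-patient rule, placebo arm | First 48 hours | Yes |
| Study drug | 48 hours | – |
| Unblinding for illness | Initial 48 hours | No |
| Monitoring for infection | Whole hospitalization | No |
| Immediate analysis of adverse events | Not limited | No threshold |
| Safety meeting for every 3 randomized infants | Whole enrolment | No threshold |
| Re-evaluation if only placebo infants become ill | Not limited in wording; follows the 48-hour unblinding sentence | No threshold |

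Only the first row ends the trial, and its window is about as long as dosing.

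**2. Inputs**

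- Placebo arm n = 15 (Methods). The protocol's planned 10 safety meetings reproduce as 30/3 = 10. It states no operating characteristic for the three-patient rule.
- Quoted rate of early-onset sepsis: 0.98 per 1000 live births (Abstract; I. Aim and Hypotheses).
- Unit record: 0 positive birth cultures in 196 (II. Background and Rationale). The one-sided 95% upper limit is 1 − 0.05^(1/196) = 0.0152, assuming that all 196 were cultured.
- Share f of early cases with onset after hour 48: not in the documents. Values of 10%, 20% and 30% are assumed for illustration.

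**3. Chance that the rule fires if every early case counts**

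With X binomial (15, p), P(X ≥ 3) = 1 − P(0) − P(1) − P(2):

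- p = 0.00098: 4.2 × 10⁻⁷
- p = 0.0152: 0.0014
- a 10% chance needs p = 0.076, which is 5.0 times 0.0152
- a 50% chance needs p = 0.174, which is 11.5 times 0.0152

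**4. Effect of the 48-hour cut**

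Replace p by p(1 − f):

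| True placebo risk p | All early cases counted | f = 10% | f = 20% | f = 30% |
|---|---|---|---|---|
| 0.0152 | 0.0014 | 0.0010 | 0.0007 | 0.0005 |
| 0.05 | 0.036 | 0.028 | 0.020 | 0.014 |
| 0.076 | 0.100 | 0.078 | 0.059 | 0.042 |
| 0.10 | 0.184 | 0.147 | 0.113 | 0.083 |
| 0.20 | 0.602 | 0.523 | 0.439 | 0.352 |

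At the 1.5% limit the loss is 0.04 percentage points (f = 10%) to 0.09 (f = 30%). At 7.6% risk with f = 10% it is 2.2 points. At 20% risk with f = 20% it is 16 points (0.602 − 0.439 = 0.163).

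**5. Limits of the sums**

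Infants are treated as independent, although multiples share an assignment. The two document rates do not describe onset after hour 48 in untreated infants: the unit figure is for birth cultures, and 190 of the 196 were treated. The rule does not define sepsis, so the event it counts may differ from the one these rates measure.

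**The case against.** The best defence is that the window follows the design. The intervention is placebo in place of 48 hours of antibiotics; study drug stops when the birth culture is reported; after that both arms have routine care. Stopping automatically on events in the treatment period, and judging later ones case by case, is coherent. In a trial of 30 infants, individual review may be more sensitive than a count of 3 in 15. This stands in part. Later cases would be seen, and the plan does not contradict itself. But the review has no criterion for ending the trial, and the team evidently wanted one numeric limit that did not rest on judgement.

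Three stronger readings are tempting, and the documents do not support them.

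- *That an onset just after hour 48 of life is certainly lost.* The rule has no anchor. Monitoring elsewhere speaks of hours of life, but the unblinding text speaks of a trial period. Because randomization follows the initial evaluation, and illness in the first 3 hours of life excludes an infant, that period could run to about hour 51. An onset at hour 50 may therefore already count. The gap is secure only for onsets clearly later, such as hour 60.
- *That the rule would often miss a stop.* If exactly three placebo infants had early sepsis, the count would fall short with probability 1 − (1 − s)³, which is 14%, 27% or 66% for late shares s of 5%, 10% or 30%. Those figures are conditional on three cases having occurred and on assumed shares. They do not measure how often the rule fails.
- *That later sepsis goes unobserved, or that disclosure is barred.* Monitoring continues through hospitalization, and nothing forbids later unblinding; the text is only silent on it. A birth culture that turns positive after 48 hours can also be read as already covered, so no gap is claimed there.

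**Conclusion.** The point holds as a minor one. The only sentence that ends the trial stops counting placebo-group sepsis at about the end of study drug, the stated unblinding for illness stops with it, and no other safeguard carries a stopping criterion. Early sepsis first showing clearly after the window, in an infant given no empiric antibiotics, does not count.

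The size is small. At the rates that the protocol quotes, the rule almost never fires under either window, and at the 1.5% limit the change in the chance of stopping is under 0.1 percentage points for assumed late shares up to 30%. It becomes material only if withholding antibiotics raises early sepsis to several times that limit. That is the situation a stopping rule exists for, and one that the unit's record, with 190 of 196 infants treated, cannot exclude. The true effect cannot be computed, because neither the risk in untreated infants nor the late share is in the documents. The case for change rests on its low cost and on the seriousness of the event, not on a large probability.

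**What to change.** Replace the stopping sentence in Monitoring with:

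> *If three infants assigned to placebo develop sepsis with onset by 72 hours of life, the trial will end; the assignment of any infant with such an event will be disclosed for this count.*

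This anchors the window to birth, extends the count and supplies the missing route to the assignment. The 72 hours is an assumption: the protocol sets no time limit for early-onset sepsis, so the investigators should confirm or change it. Dosing, the 48-hour stop of study drug and bedside care stay as they are.

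The cost is a one-sentence amendment. No new data are needed, because infants are already monitored for infection throughout hospitalization. There are two small downsides: an occasional early hospital-acquired infection may count towards stopping, and an infant with sepsis between 48 and 72 hours would have the assignment disclosed, by which time study drug has ended.
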